This study (Figures 1 and 3) will include Option A consisting of 9 lab visits each approximately 2 hours long, except visit 1, which will last up to 3 hours **OR** Option B consisting of 5 lab visits each containing 2 vaping sessions separated by a 3-hour washout period and lasting approximately 6 hours. Figure 2 illustrates the study e-cig and e-liquid variations. Figure 3 depicts the sequence of the proposed study. We will conduct an experimental study examining how the manipulation of nicotine form (nicotine salt (NSB) vs. free-base (FB)) influences vaping behavior, abuse liability, toxicant exposure and heart and lung health.

Evaluating E-Cigarette Nicotine Form, Concentration, and Flavors among Youth

Figure 1. Vaping Session

Vaping Session	
12 hour nicotine abstinence	
Start of Session:	Surveys Respiratory Measures Cardiovascular Measures Blood Draw (0 min)
STD Puffing (5 min):	Blood Draw (5 min) Surveys
Ad-lib Puffing (30 min): Blood Draw (10 min) Blood Draw (35 min) Surveys	
3-hour washout (Visits 2-5 between vape sessions) (Option B Only)	
3 hrs. post exposure:	Respiratory Measures Cardiovascular Measures (Option B Only)
1 vaping session will occur at each visit for 9 visits (Option A Only)	
1 vaping session will occur at the first visit / 2 vaping sessions will occur at the final 4 visits (Option B Only)	

Figure 2. E-cig and e-liquid for Vaping Sessions

[figure not shown]
[figure not shown]

Figure 3. Study Sequence Option A and Option B

Evaluating E-Cigarette Nicotine Form, Concentration, and Flavors among Youth

ii. Study Procedures

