
1. Recruitment Feasibility and Retention

a) Recruitment

We intend to recruit 130 e-cig users from the community over an 18-month period and have them complete nine study visits (Option A) or five study visits (Option B); therefore, we need 3-4 participants to be recruited and complete study procedures per month.

We are confident our recruitment approach, laboratory facilities, and equipment redundancy will result in a sufficient participant processing rate, given our successful completion of other tobacco-related research of similar design⁴¹. E-cig users will be recruited from advertisements through a variety of media outlets and the internet, including Study Search, as well as community events. Participants from

Evaluating E-Cigarette Nicotine Form, Concentration, and Flavors among Youth

other studies who have agreed to be contacted regarding other study opportunities will also be contacted. Staff from those studies will prepare contact letters/emails and call participants on behalf of this study. Interested participants will be referred to this study for screening. Participants will access the screening questionnaire using a public survey link generated by REDCap. Based on our team's previous studies, we conservatively assume a 20% attrition rate. Thus, we need to recruit 130 participants to have 60 complete the study. Participants who meet the following eligibility criteria will be asked to take part in the study.

Inclusion criteria: 1) a current e-cigarette user (≥ 1 vaping bout per day) for at least the past 3 months , 2) 21-25 years old, 3) willing to abstain from all tobacco and nicotine for at least 12 hours prior to lab sessions, 4) willing to complete nine lab visits/vaping session lasting up to 2 hours each or five lab visits lasting up to 6 hours each (except Visit 1) , 5) able to read and speak English, 6) willing to provide informed consent

Exclusion criteria: 1) self-reported diagnosis of lung disease including asthma, cystic fibrosis, or chronic obstructive pulmonary disease, 2) history of cardiac event or distress within the past 3 months, 3) currently pregnant (determined using urine pregnancy test), planning to become pregnant, or breastfeeding, 4) use of other tobacco products >10 days in the past month, 5) current marijuana use >10 times per month, 6) currently engaging in a vaping cessation attempt.

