Nevertheless, all participants will be screened for general medical precautions (pregnancy, cardiovascular disease) and monitored for adverse events during the study period. Study personnel will assess for adverse events via self-report at all follow-up visits. Any serious adverse events will be reported to the study's DSMB, and then to the OSU IRB and to the NIH. We will withdraw participants who have a serious adverse event, or become pregnant, begin to breastfeed, or have a cardiovascular or pulmonary event during the study. The most likely adverse (potential for nicotine overdose) event is anticipated to be rare (<5% in our team's previous studies) and mild (nausea, headache, disrupted sleep), and will be handled quickly (i.e., advice to participant to reduce or stop e-cig use). Lab studies of toxin exposure suggest that e-cigs incur no greater risk to health than do conventional cigarettes. Indeed, e-cigarettes generally show lower levels of harmful and potentially harmful constituents. To date, e-cigarette studies discussing adverse events report mild and tolerable side effects that generally resolved completely over time with continued use; the most predominant of which were mouth/throat irritation, cough, and headache. In four randomized clinical trials, no serious adverse events were reported, and the e-cigarette group and the nicotine patch group had comparable levels of adverse events in two studies. The most common were mouth irritation, throat irritation, dry cough and headache. Following the completion of the study, we will encourage all participants to quit their use of e-cigarettes.

2. Loss of Confidentiality and Privacy:

Risks

There is a risk of breach of confidentiality or a loss of privacy associated with taking part in the study.

Protections

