The data and safety monitoring plan will involve the continuous evaluation of safety, data quality and data timeliness. Investigators will conduct continuous review of data and patient safety at their regular Disease Group meetings (at least monthly). The PI of the trial will review toxicities and responses of the trial where applicable at these disease center meetings and determine if the risk/benefit ratio of the trial changes. Frequency and severity of adverse events will be reviewed by the PI and compared to what is known about the agent/device from other sources; including published literature, scientific meetings and discussions with the sponsors, to determine if the trial should be terminated before completion. Serious adverse events and responses will also be reviewed by the OSUCCC Data and Safety Monitoring Committee (DSMC). The PI will also submit a progress report (biannually for Phase II and quarterly for Phase I) that will be reviewed by the committee per the IRB of record as per the policies of the IRB. All Serious Adverse Events are to be submitted to the DSMC for their review. Submissions are made via OnCore.

Adverse Events

Adverse events will be assessed by study staff at each visit via participant self-report and managed immediately. All adverse events will be reported to the OSU IRB. We will monitor for risk of smoking/vaping by screening participants for general medical precautions (pregnancy, cardiovascular disease). Any adverse events, breaks of confidentiality, or any other data or safety issues that arise will be discussed immediately between study personnel and [name]. [name] will be responsible for completing an Adverse Events Form should an event occur. [name] will report Serious Adverse

Evaluating E-Cigarette Nicotine Form, Concentration, and Flavors among Youth

Events to the OSU IRB within 24 hours of having received notice of the event. [name] will gather any information needed to investigate the event and to determine subsequent action. Any subsequent action will be documented and reported to the OSU IRB and the Program Officer at NIH. Adverse event reports will be reviewed annually with the OSU IRB to ensure participant safety.

Collection of Adverse Events

The collection of adverse events will be on a self-report basis and logged within an electronic data capture system (REDCap) or collected using standardized paper forms and will only be identified with the study ID of the participant.

I. Addendum

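### Adverse events are asked about only at visits, so events that start after the last attended visit are not actively sought, in completers or in dropouts

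*Combined protocol and SAP*

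**What the plan says.** Two places say when adverse events are asked about. Section H (Adverse Events): "Adverse events will be assessed by study staff at each visit via participant self-report and managed immediately". Section G.ii.1 (Risk of Using ECs, Protections): "Study personnel will assess for adverse events via self-report at all follow-up visits". The mode is given under Collection of Adverse Events in Section H: "The collection of adverse events will be on a self-report basis and logged within an electronic data capture system (REDCap"), or on paper forms.

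The schedule is in Figure 1 (Section D.i). Option A: "1 vaping session will occur at each visit for 9 visits (Option A Only"). Option B: "1 vaping session will occur at the first visit / 2 vaping sessions will occur at the final 4 visits (Option B Only"). Table 1 has no column after visit 9 or visit 5, and neither Figure 1 nor Table 1 lists an adverse-event query. No separate follow-up visit is defined. The only contacts described outside visits are appointment reminders (Section D.ii.1.b).

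Section G.ii.1 expects the most likely adverse event to be "rare (<5% in our team's previous studies) and mild (nausea, headache, disrupted sleep"). Section G.ii.3 adds infection at the blood-draw site. Between visits 1 and 2, participants also use a study pod at home, unsupervised (Section D.ii).

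Under Section H.ii, the PI reviews the frequency and severity of adverse events to judge whether risk/benefit has changed and whether the trial should be terminated.

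**The concern.** Some of the risks that the protocol names show themselves only after the participant has gone home. Disrupted sleep cannot be observed in a session of about 2 hours or a visit of about 6. An infection at the draw site would also emerge later, and blood is sampled at every session, including the last. Under a visit-only rule, such an event is asked about only if the participant comes back. Two groups are left without a later question: completers after their final visit, and anyone who stops attending, including a person who leaves during the take-home practice period.

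Option B has a second, smaller weakness. Visits 2 to 5 each hold two liquids separated by a 3-hour washout. The plan gives no rule for recording onset time or for assigning an event to a session. An event reported at the next visit may then not be traceable to either liquid.

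What is at stake is the completeness of the adverse-event record behind the PI's risk/benefit and termination review. No efficacy or exposure comparison is at stake.

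**Working it through.** The plan states no figure for this gap, so there is none to reproduce. The check counts sessions and participants.

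**Inputs.** Visits and sessions per option: Figure 1. Eight study liquids, and visit 1 on the participant's own device: Section D.ii. 60 completers, 130 recruited and 20% attrition: Section D.ii.1.a, where the basis is "Based on our team's previous studies, we conservatively assume a 20% attrition rate". Latin-square order: Section E.ii. Expected event rate below 5%: Section G.ii.1. The A/B split is not given, so ranges are shown.

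1. Sessions per completer.
   - Option A: 9 × 1 = 9. Option B: 1 + 4 × 2 = 9.
   - Less the own-device session, each option has 8 study-liquid sessions. For 60 completers: 60 × 8 = 480.

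2. Study-liquid sessions with no later visit.
   - Option A: 1/8 = 12.5%; if all choose A, 60 × 1 = 60 of 480.
   - Option B: 2/8 = 25%; if all choose B, 60 × 2 = 120 of 480.
   - If the Latin square is balanced by position (an assumption), this is 60/8 = 7.5 to 120/8 = 15 sessions per liquid, evenly spread.

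3. Study-liquid sessions whose next-visit report covers that study session alone.
   - Option A: 7 of 8 (visits 2 to 8).
   - Option B: 0 of 8. Six are followed by a visit but share the report with a second liquid, and two have no later visit.
   - Events that start during the 3-hour washout can still be tied to the first liquid. The text describes no bar on own-product use between visits beyond the 12-hour abstinence, so even Option A reports are not a clean record of one liquid.

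4. Dropouts.
   - 60/(1 − 0.20) = 75 recruited, so 75 − 60 = 15 dropouts.
   - The stated 130 does not follow from 20%: 130 × 0.80 = 104 completers, not 60. Taken literally, 130 recruited and 60 completing is 70 lost, or 70/130 = 53.8%. That inconsistency is a separate matter; 15 is used here.
   - Participants who return for visit 2 are asked then about the practice period. Only those who leave before visit 2 are missed for it.

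5. Rough scale in events among completers. The unit of the <5% figure is not stated, so both readings are shown, using 5%.
   - Per participant, one event each, spread evenly over 8 sessions: 60 × 0.05 = 3 events; 3 × 0.125 = 0.375 to 3 × 0.25 = 0.75 fall in sessions with no later visit.
   - Per session: 60 × 0.05 = 3 to 120 × 0.05 = 6.
   - On either reading these are upper limits for that class of event, because events that start before departure can still be recorded at the visit.

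**The case against.** The strongest reply is that the plan is less closed than the visit rule suggests. Section G.ii.1 has participants monitored throughout the study period. Section H says that issues are discussed immediately when they arise, and the clock for serious events runs from notice rather than from a visit: "Events to the OSU IRB within 24 hours of having received notice of the event". Consent and contact pages, where an instruction to report events might stand, are not in the available text. This stands in part. A reader might infer that delayed events after the last visit are never collected, but the documents support only that they are not actively asked about.

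Three further inferences are tempting and also fail.

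- That per-liquid tolerability is a safety output of the trial. Adverse events are not in the aims, in Table 1 or in Section E, and the PI's review is not described as being by liquid.
- That the harsher liquids will look safer. A position-balanced Latin square would spread the final-visit loss evenly over liquids. Selective loss could come only from dropout, and neither its presence nor its direction is shown.
- That Option B allows only one query per visit. Section H sets neither the number nor the timing of queries, and the visit checklists mentioned under Quality Assurance (Section D.ii.3) are not shown.

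It is also fair to say that these are supervised sessions in existing daily users, that the expected events are mild, and that the counts above are of sessions, not lost events. That limits the consequence. It does not supply the missing contact: nothing in the available text schedules a question after the last attended visit.

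**Conclusion.** The gap is real and narrow. As written, 12.5% (all Option A) to 25% (all Option B) of completers' study-liquid sessions have no later adverse-event question. Nor does the last attended session, or an unfinished practice period, of anyone who leaves. The dropout count of about 15 assumes that 20% attrition applies to 75 recruited. A reader might take 20% of 130, or 26, but that would leave 104 completers and does not fit the planned 60.

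The effect is a modest under-count in the adverse-event frequency and severity that the PI reviews, plus weak attribution in Option B. The hypotheses and planned analyses are untouched. The conclusion rests on the visible text. An instruction to report events in the removed pages would ease the gap, but would not by itself make the collection active. The change is worth making because it supports safety monitoring at very little cost.

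**What to change.** Amend the adverse-event wording in Section G.ii.1 (Protections) and Section H (Adverse Events, Collection of Adverse Events) to state:

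- One adverse-event query by REDCap link, text or call about 48 hours after the last attended visit, for completers and for anyone who misses a visit or withdraws, including during the practice period. Forty-eight hours matches the protocol's own minimum gap between visits; events with later onset would still depend on volunteered reports.
- A query at the end of each vaping session (in Option B, before the second liquid starts) and at the start of the next visit.
- Session number, liquid code, and onset date and time recorded for each event.

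In Option B this attributes events that start before the second liquid. Events that start after both liquids remain ambiguous even so, and should be logged against both.

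The cost is protocol wording, a few extra fields on the REDCap form, and one message per participant through the existing reminder channels. It takes a few minutes per session, and some participants will not answer the final message. No new visit, procedure or staff is needed.

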While the long-term health effects of e-cigarettes are still unclear, studies examining proximal biomarkers of health indicate that e-cig users are exposed to many cardiovascular and pulmonary toxicants, including carcinogens, such as carbonyls, furans, reactive oxygen species, and heavy metals^{6,7}. Early evidence indicates that e-cig users experience adverse health effects, including increased oxidative stress, respiratory and mucosal inflammation, arterial stiffness and altered hemodynamics and platelet activity⁸. Moreover, use of nicotine by youth can adversely affect attention, learning, and memory, as well as lead to increased impulsivity. Taken together these data suggest that sustained e-cig use will likely have notable adverse health effects⁹. Since their introduction in 2015, to our knowledge, no studies have examined the toxicological and physiological effects of NSB device use, nor the impact of nicotine form. Previous research has largely focused on free-base nicotine devices, with only a few focusing on pulmonary and cardiovascular effects.

The youth vaping epidemic in the U.S. is drawing serious concern from parents, schools, health officials and regulators. There is now a wave of support and a need to create effective e-cig policies and regulations to prevent further proliferation of youth e-cig use. One of the most effective policies may be to create a product standard for nicotine to reduce the palatability and abuse liability of e-cigs for youth;

Evaluating E-Cigarette Nicotine Form, Concentration, and Flavors among Youth

however, strong scientific evidence is needed for the FDA to impose such regulations. The proposed project will begin to address this need.

A. Specific Aims

Utilizing a human laboratory design, we will examine the influence of nicotine form and concentration, and e-liquid flavor on youth vaping behavior, nicotine uptake, abuse liability, toxicant exposure, and acute cardiovascular and pulmonary effects. H1a: Nicotine salt (vs. free-base) and menthol flavored e-liquids (vs. tobacco flavored) will result in puffs of longer duration and higher flow rate, and a greater total inhaled aerosol volume, and H1b: demonstrate greater nicotine uptake, abuse liability, and adverse cardiovascular and pulmonary effects. H1c: High concentration, free-base nicotine (vs. salt nicotine) will result in puffs of shorter duration, lower flow rate, less volume, and lower abuse liability.

B. Significance

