Markers of endothelial dependent and independent function will be measured by B-mode ultrasound⁴⁴. Arterial stiffness, blood pressure, and heart rate will be measured at baseline. Arterial stiffness and vascular reactivity will be measured with pulse wave velocity (Vicorder or similar) and pulsewave-analysis (AiX75, SphygmoCor, or similar)⁴⁵. Inflammation will be measured by plasma levels of IFN- β , IL-1 β , IL-17, TNF- α as well as markers of oxidative stress, including OxLDL and Malondialdehyde⁴⁶. Laboratory spirometry, airway inflammation, and airway reactivity⁴⁷⁻⁴⁹ will be measured. Laboratory Spirometry will be conducted in a standing position and according to the recommendations of ATS Clinical Guidelines⁴⁷. Forced expiratory volume (FEV1), forced vital capacity (FVC), and FEV1/FVC. Airway Inflammation will be assessed using exhaled nitric oxide via the NIOX VERO. The current literature shows immediate changes in airway inflammation immediately follow e-cig use⁴⁸. Airway Reactivity will be measured via TremoFlo, which is a well validated measurement of central obstruction, peripheral obstruction, and dynamic collapse⁴⁹ and provides curves of Resistance (R) and Reactance (X) as well as parameters reflecting large and small airway function. The current literature show an increase in impedance, respiratory resistance and overall peripheral airway resistance following e-cig use⁴⁸.

In visit 1, which will last up to 3 hours, participants will use their own e-cig and e-liquid and participate in a single vaping session. After visit 1, participants will take home a study e-cig device and 1 weighed pod pre-filled with tobacco flavored e-liquid (the participant is randomized to at the end of visit 1) to practice (20 puffs per day with the study device and until the participant feels comfortable) using the device before visit 2. Practice use with the study e-cig device and pre-filled pod will be verified based on data downloaded (via eScribe) from the device during visit 2. After visit 1, for the subsequent visits

Evaluating E-Cigarette Nicotine Form, Concentration, and Flavors among Youth

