Laboratory Spirometry (SpiroLab)	X	X
Airway Inflammation (NIOX VERO)	X	X
Airway Reactivity (TremoFlo)	X	X
Cardiovascular Measures		
Vascular Reactivity (Vicorder or similar)	X	X
Blood Pressure	X	X
Heart Rate	X	X
Markers of endothelial dependent and independent function		
B-mode ultrasound (Vicorder or similar)	X	X
Arterial stiffness		
Pulse wave velocity and analysis (Vicorder or similar)	X	X

Evaluating E-Cigarette Nicotine Form, Concentration, and Flavors among Youth

E. Statistical Methods

Generalized linear mixed models will be employed to identify associations of nicotine form, nicotine concentration, and flavoring with various outcome measures (e.g., plasma nicotine, spirometry, flow-mediated dilation). Models will include relevant covariates (e.g., gender), a random effect for participant, main effects for nicotine form and concentration, and the interaction between nicotine form and concentration and nicotine form and flavor. Because of multiple measurements tested, we will assume a significance threshold corresponding to one expected false discovery per 100 tests ($p=0.01$).

i. Power Analysis

This study, for each of the main effects and $\alpha = 0.01$, achieves 80% power to detect an effect size of 0.5 standard deviations of the paired differences. For interaction effects, we will estimate 80% power (effect size 0.5 SD) to distinguish between any two of the interaction groups (e.g., free base/low nic, free base/high nic), while correcting for the pairwise tests ($p=0.01/6=0.0017$). Carryover and period effects will also be examined.

ii. Data Analytic Plan

Because product sampling will be randomized using a Latin Square, a fixed effect for session and a random effect for sequence will be included in all analyses.

iii. Missing Data

While we will make every effort to minimize the missing data for this study, missing data can arise due to various reasons. Violation of missing complete at random (MCAR) will be checked by evaluating whether any covariates are associated with missing data. If so, these covariates will be subsequently included and controlled for in the GLMM model. Our primary analysis will use mixed models which assumes Missing At Random (MAR) to deal with the missing data problem. In addition, sensitivity analyses will also be conducted using results from multiple imputation and complete cases strategies.

F. Gender/Minority/Pediatric Inclusion for Research

i. Inclusion of Women and Minorities

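### Adverse events are found by self-report only, and no rule says whether or when an abnormal blood pressure, heart rate or spirometry value is reviewed and logged as one

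*Combined protocol and SAP*

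**What the plan says.** Three statements describe how adverse events are found, and all three name the participant's own report:

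- Section G.ii.1 (Risk of Using ECs, Protections): "Study personnel will assess for adverse events via self-report at all follow-up visits".
- Section H, Adverse Events: "Adverse events will be assessed by study staff at each visit via participant self-report and managed immediately".
- Section H, Collection of Adverse Events: "The collection of adverse events will be on a self-report basis".

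Heart and lung function are measured separately. Table 1 marks spirometry, airway reactivity, blood pressure and heart rate at visit 1 and at every later visit under both schedules, and section D.ii.2.a repeats the measures for the eight test liquids. On timing, section D.ii.2.a says: "Arterial stiffness, blood pressure, and heart rate will be measured at baseline". Figure 1 puts respiratory and cardiovascular measures at the start of a session and again 3 hours after exposure, the latter labelled for Option B only.

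Two decisions draw on safety information. Under section H the PI reviews how frequent and severe adverse events are, compares this with outside sources, and considers whether to end the trial early. Under section G.ii.1 participants are withdrawn if they have a serious adverse event, become pregnant, begin to breastfeed, "or have a cardiovascular or pulmonary event during the study".

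**The concern.** H1b in section A expects nicotine salt and menthol liquids to "demonstrate greater nicotine uptake, abuse liability, and adverse cardiovascular and pulmonary effects". Changes in blood pressure, heart rate or airflow need not be felt, so a participant's report is a weak detector in the area where the trial is looking for harm. The trial already takes objective readings there, but the text uses them only as study measures and model outcomes. Section E, for example, names spirometry among the outcomes.

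At stake is the completeness of the adverse-event record. If an abnormal reading without a complaint has no stated path into the log, it may not reach the IRB as an adverse event, and it may not enter the frequency and severity that the PI reviews. The withdrawal rule is also hard to apply consistently, because the event it refers to is not defined and no method of detecting it is given.

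**Working it through.** The plan gives no figure to reproduce, and the point depends on no power, alpha or rate. The check sets the relevant texts side by side.

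1. **Is there a second source of adverse events?** All three statements name self-report and none adds another source. Table 1, the session procedures in D.ii.2.a, the measures in D.iii and the statistical section give no limit, no same-day review, and no rule that turns a measured value into an adverse event.

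2. **Is there another route?** There are three general ones:
   - section H has data and patient safety reviewed at least monthly, and has the PI review toxicities and the risk/benefit ratio;
   - section H also has other data or safety issues discussed immediately with a responsible person, who completes an Adverse Events Form if an event occurs;
   - section D.ii.3 has weekly staff meetings that cover data monitoring results.

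   None of these mentions the physiological values, or says who judges them, when, or against what.

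3. **What could the recorded values show?** This depends on when they are taken (the Option B label in Figure 1 is read here as covering both the respiratory and the cardiovascular line):

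| Schedule | Start-of-session reading | Reading 3 hours after exposure |
|---|---|---|
| Option A | yes | none stated |
| Option B | yes | yes |

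4. **How many sessions are involved?** 60 completers x 9 sessions = 540 planned sessions. Of these, 60 x 1 = 60 use the participant's own device and 540 - 60 = 480 use a test liquid. This is not a count of post-exposure readings. The documents do not say how many participants take each option, and if all took Option A the number of stated post-exposure readings would be zero.

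5. **Which liquid goes with a reading?** A start-of-session value precedes that session's liquid, so it cannot be attributed to it. In Option A the previous study session was at least 48 hours earlier. Abstinence is required for the last 12 hours, which leaves at least 48 - 12 = 36 hours in which the documents do not bar use of the participant's own device. The most recent liquid is therefore context for the reading, not a demonstrated cause.

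**The case against.** The strongest case against the point is that a collection method is not a definition. The documents never define an adverse event, so they do not say that a silent abnormal reading fails to be one. The immediate-discussion clause covers data as well as complaints and is not tied to self-report. Operating procedures and visit checklists are mentioned in D.ii.3 but are not part of these documents and may cover the matter. H1b is a comparison between liquids, tested on measured outcomes; it does not predict clinical events in individuals.

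Much of this stands, and it rules out several stronger readings that a reader might infer:

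- **That measured values can never become adverse events.** The text does not forbid it, and the general clauses leave a route open.
- **That a silent harm goes unrecorded.** The values are recorded and used as outcomes. What may be missing is the adverse-event entry and the reporting that follows from it.
- **That a participant can finish between two monthly reviews.** The shortest spans are (9 - 1) x 2 = 16 days in Option A and (5 - 1) x 2 = 8 days in Option B. These are minimums, because visits are at least 48 hours apart, and the weekly meetings and immediate discussion do not wait for the monthly review.
- **That the adverse-event frequency is biased low by a known amount.** No figure in the documents supports a size, and early termination does not rest on frequency alone.

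The objection does not supply a rule. Each general provision leaves it to discretion whether an abnormal reading is examined and logged, while the specific collection sentence names self-report and nothing else.

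**Conclusion.** The point holds as a gap in a stated collection rule. Self-report is the only named source of adverse events, the readings taken at every visit are not linked to the log, and the event that triggers withdrawal is undefined. A symptomless abnormal value may therefore be absent from the record that the PI reviews.

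The number of such omissions cannot be estimated from the documents. The conclusion assumes that the protocol text governs and that no unseen operating procedure fills the gap; if one does, the protocol should refer to it. The gap does not affect the comparisons between liquids, which use the measured values directly. It should be closed before further enrolment, and it does not invalidate the trial.

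**What to change.** In section H, Collection of Adverse Events, replace the self-report wording with: *by self-report and from the blood pressure, heart rate and spirometry values already recorded at each session*. Then:

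1. Have the investigators set the review limits in advance and name who reviews flagged values and when. No limit is proposed here.
2. Set REDCap to flag a value outside those limits at entry.
3. Log each flagged value with the time of the reading and the most recent liquid used before it, not the liquid about to be used.
4. Include these entries in the frequency and severity that the PI reviews.
5. Reconcile the withdrawal wording in section G.ii.1 with this rule, and say how the event it refers to is defined and detected.
6. Acknowledge in the protocol that Option A has no stated post-exposure heart or lung reading. There the change captures only start-of-session values, so an acute change after vaping could still be missed.

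The cost is protocol text and a range flag in the database, with no new measurement. The downside is some false alarms to document.
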